11.1. Participant Completion

This study will be defined as complete when all study procedures are completed, including the follow-up phone call to assess any adverse events.

11.2. Participant Stopping Rules and Withdrawal Criteria

Participants may be prematurely terminated from the study for the following reasons:

1. The participant elects to withdraw consent from all future study activities, including follow-up.
2. The participant is “lost to follow-up” (i.e., no further follow-up is possible because attempts to reestablish contact with the participant have failed).
3. The participant dies.
4. The Investigator no longer believes participation is in the best interest of the participant.

11.3. Participant Replacement

Participants who withdraw or are withdrawn will be replaced.

11.4. Follow-up after Early Study Withdrawal

If a participant is withdrawn from the study for any reason, the participant may be asked to complete a final visit by phone to assess any adverse events after AMT application. During this phone call, subjects will be asked about any adverse events (including serious adverse events) since their last visit, as well as how their eczema is currently doing. Any subject with an ongoing adverse event (including serious adverse event) at the time of this phone contact will continue to be followed by study personnel until resolution of the event. Should the subject withdraw prior to completion of 7 days of cream application, subject will be asked to return to the clinic in order to return aliquots of unused and used cream as well as to assess any adverse events after AMT application. Should subjects experience an adverse event, subject will continue to be followed until resolution of the event as in above.

11.5. Study Stopping Rules

The study may be prematurely terminated for the following reasons:

Rules for stopping the entire study will include:

- Any serious adverse event for which there is a reasonable possibility that the study product caused the serious adverse event.
- The development of a serious adverse event for which attribution cannot be assessed as definitely unrelated to the study product in 10% or more of the study population.
- The development of any severe (Grade 3) adverse events in 10% or more of the study population.

If any of these criteria for halting the study are met, the study will not be resumed until the relevant information has been discussed with the FDA and the FDA concurs with resumption of the study.

12. Safety Monitoring and Reporting

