3.1. Description of Study Design

This is a single site, double blind placebo controlled study, which will assess the efficacy, safety, and steady state of Autologous Microbiome Transplant (AMT) cream in adults with AD. After providing informed consent, patients will be assessed for study eligibility at the screening visit, in which participants will consent to all of the study experiments separately. Subjects that withdraw from the study will be replaced. Eligible subjects will be randomized to receive either AMT cream or placebo in a 2:1 allocation ratio (AMT cream: placebo).

Subjects will be instructed to apply either the AMT or vehicle cream to both arms twice a day for seven days. Both subjects and clinical investigators will be blinded. Optional follow-up visits to assess clinical effect and steady state may occur at 1 and 4 hours after initial cream application if the subjects are willing to return at these time points. 4 days after the treatment visit, subjects will return to the clinic for fresh aliquots of the AMT and vehicle creams as well as to assess safety and clinical effect. Subjects will return to clinic after the seven day course of AMT or vehicle creams for clinical and safety assessments. Subjects will then be asked to return to the clinic 1 day after completion of the AMT or vehicle cream course for additional safety and clinical effect assessments. Subsequently, subjects will return for additional follow-up visits only if their lesional atopic dermatitis sites have not yet returned to baseline (*S. aureus* is no longer inhibited and *Staph species* from the AMT cream is zero). Up to 27 subjects will be recruited for this entire study. The duration of this study is approximately 2 months. We anticipate the entire study duration will be approximately 2 years total, and that it will take approximately 1 year to reach recruitment and enrollment goals for this study. The study flow diagram is provided in Figure 1.

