4.2. Inclusion Criteria

Up to 54 subjects with atopic dermatitis will be enrolled in this study. Enrollment will not take race or gender into consideration. Pregnant women, children (under age 18), and unhealthy subjects with significant co-morbid conditions as determined by the PI will be excluded.

1. Male or female subjects who are not pregnant or lactating. Female subjects of child-bearing potential must have a negative urine pregnancy test on the day of the screening visit in order to be eligible for the study.
2. 18-60 years of age
3. Diagnosis of atopic dermatitis for at least 6 months using the Hanifin and Rajka Diagnostic Criteria for atopic dermatitis
4. Presence of lesional atopic dermatitis skin in both antecubital fossae
5. Positive *S. aureus* colonization based on results of a skin culture taken from one of their AD-affected antecubital fossae during the screening visit
6. Positive for antimicrobial CoNS species from non-lesional AD skin

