12.2 Definitions

An adverse event (AE) is any untoward medical occurrence in a subject during participation in the clinical study or with use of the experimental agent being studied. An adverse finding can include a sign, symptom, abnormal assessment (laboratory test value, vital signs, electrocardiogram finding, etc.), or any combination of these.

A serious adverse event is defined by regulatory agencies as one that suggests a significant hazard or adverse event, regardless of the investigator or sponsor's opinion on the relationship to investigational product. This includes, but may not be limited to, any event that (at any dose):

- is fatal
- is life threatening (places the subject at immediate risk of death)
- requires in-patient hospitalization or prolongation of existing hospitalization
- results in persistent or significant disability/incapacity
- constitutes a congenital anomaly/birth defect
- is medically significant, in that it may jeopardize the subject and may require medical or surgical intervention to prevent one of the outcomes listed above.

Any event that does not exactly meet this definition, but in the investigator's opinion represents a significant hazard (eg, emergency room visit or outpatient surgery), can be assigned the "other significant hazard" in regards to reporting serious criteria.

Additionally, important medical events that may not be immediately life threatening or result in death or hospitalization but that may jeopardize the subject or require intervention to prevent one of the outcomes listed above, or result in urgent investigation, may be considered serious. Examples include allergic bronchospasm, convulsions, and blood dyscrasias.

All subjects will receive verbal and written instructions with site contact information for whom to contact if they experience an AE associated with study procedures performed for this protocol or if the subject resumes their protocol-prohibited medication during the washout period.

EXPECTED RISKS

Risks of applying microbial cream (Cetaphil® Moisturizing Lotion mixed with the subject's endogenous bacteria):

1. Skin infection

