12.3 Grading and Attribution of Adverse Events

12.3.1 Grading Criteria

Clinical investigators will “grade” the severity of all AEs using the following scale; the results will be reported on the SAE form, if necessary.

1 = MILD – aware of sign or symptom, but easily tolerated

2 = MODERATE – discomfort enough to cause interference with usual activity

3 = SEVERE – incapacitating with inability to work or do usual activity

4 = LIFE-THREATENING – refers to an event in which the patient was, in the view of the investigator, at risk of death at the time of the event. It does not refer to an event which hypothetically might have caused death if it were more severe.

5 = FATAL

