12.3.2 Attribution Definitions

The relationship, or attribution, of an adverse event to the study therapy regimen or study procedure(s) will initially be determined by the site investigator and recorded on the appropriate AE/SAE CRF. Final determination of attribution for safety reporting will be determined by NIAMS. The relationship of an adverse event to study therapy regimen or procedures will be determined using the descriptors and definitions provided in Table 12.3.2.

Table 12.3.2 Attribution of Adverse Events

Code	Descriptor	Relationship (to primary investigational product and/or other concurrent mandated study therapy or study procedure)
UNRELATED CATEGORY		
1	Not related	The adverse event is clearly not related: there is insufficient evidence to suggest a causal relationship.
RELATED CATEGORIES		
2	Possibly/ Probably	The adverse event has a reasonable possibility to be related; there is evidence to suggest a causal relationship.
3	Definitely related	The adverse event is clearly related.

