12.5 Reporting of Serious Adverse Events and Adverse Events

Recording and Reporting Obligations for SAEs

The investigator will provide the IRB appropriate information concerning any findings that suggest there has been an SAE related to the study.

The investigator will notify the UCSD Human Research Protections Program of any unexpected, fatal or life-threatening experiences in writing no later than 10 working days of the event, according to standard IRB procedures. All serious and medically significant adverse events considered related to the product by the investigator will be followed until resolved or considered stable.

All SAE's will undergo expedited reporting to the NIAMs and the Independent Safety Officer through KAI within 48 hours of the investigator becoming aware of the event.

SAEs that are unanticipated, serious, and possibly related to the study intervention will be reported to the IRB, FDA, and Independent Safety Officer in accordance with requirements. For the IND/IDE:

- 7-day IND Safety Report (unexpected fatal or life-threatening AEs related to the intervention); a copy of the report sent to the FDA will be submitted to the Independent Safety Officer within 24 hours of FDA notification.
- 15-day IND Safety Report (any other serious and unexpected AE related to the intervention); a copy of the report submitted to the FDA will be submitted to the Independent Safety Officer within 24 hours of FDA notification.
- Other AEs documented during the course of the trial will be included in the annual IND report. In the annual AE summary, the Independent Safety Officer Report will state that they have reviewed all AE reports.

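### The severity-based halting criterion stops at Grade 3, so definitely unrelated Grade 4 or 5 events count toward no halting rule while definitely unrelated Grade 3 events do

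*Combined protocol and SAP*

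**What the plan says.** Section 11.5 (Study Stopping Rules) lists three criteria for halting the whole study.

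1. Any single serious adverse event with a reasonable possibility of having been caused by the product.
2. A "serious adverse event for which attribution cannot be assessed as definitely unrelated to the study product in 10% or more" of the study population.
3. "The development of any severe (Grade 3) adverse events in 10% or more of the study population".

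The same three items return as triggers for ad hoc review in Section 12.8.2.2, and as events that could suspend enrolment and dosing in Section 12.8.2.2.1. The third item is worded identically each time.

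The grading scale in Section 12.3.1 has five levels. Grade 3 is severe, defined by incapacity for work or usual activity. Grade 4 is life-threatening and "refers to an event in which the patient was, in the view of the investigator, at risk of death at the time of the event". Grade 5 is fatal. In Section 12.2 an event is serious if, among other things, it is fatal or "is life threatening (places the subject at immediate risk of death").

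The attribution table in Section 12.3.2 has one unrelated code. It covers events that are clearly not related, which it explains by saying that "there is insufficient evidence to suggest a causal relationship".

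**The concern.** A halting rule based on severity would be expected to count every event at or above the stated grade. This one names a single grade in the middle of the scale and leaves out the two worse ones.

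That matters because the third criterion is the only one that does not depend on a causality judgement. Criteria 1 and 2 can reach Grade 4 and 5 events, but both let go of an event once it is called definitely unrelated. Criterion 3 would be the natural place to catch such events. As worded, it catches the less severe ones only. At stake is whether the automatic halt applies, not whether anyone learns of the event.

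**Working it through.** The plan gives no figure to reproduce here. The check is to run each kind of event through the three criteria and then see what the 10% threshold means in subjects.

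**Step 1: which criteria can count an event.** Grade 4 and 5 events are serious under Section 12.2. The Grade 3 row takes a non-serious event; a serious one could also count under criteria 1 and 2, according to its attribution.

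| Event | Reasonable possibility of relation | Coded not related, but cannot be called definitely unrelated | Definitely unrelated |
|---|---|---|---|
| Grade 3, non-serious | Criterion 3 | Criterion 3 | Criterion 3 |
| Grade 4 | Criterion 1 at one case; also 2 | Criterion 2 | None |
| Grade 5 | Criterion 1 at one case; also 2 | Criterion 2 | None |

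The gap is the last column for Grades 4 and 5. Read literally, such events meet no criterion at any count, even 27 of 27.

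The middle column rests on reading the single unrelated code as covering some events for which evidence is merely lacking. If the site treats that code as meaning definitely unrelated, those events also escape criterion 2 and the gap is wider.

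**Step 2: the threshold in subjects.** The plan does not define the study population for this rule. It gives two totals: Section 3.1 says "Up to 27 subjects will be recruited for this entire study" and Section 4.2 says "Up to 54 subjects with atopic dermatitis will be enrolled in this study" (Section 13.1 also gives 54). Assuming the planned total is the denominator, the smallest count that meets the rule is 0.10 × N rounded up:

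- N = 27: 0.10 × 27 = 2.7, so 3 subjects. 3/27 = 11.1%; 2/27 = 7.4%.
- N = 54: 0.10 × 54 = 5.4, so 6 subjects. 6/54 = 11.1%; 5/54 = 9.3%.

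**Step 3: the effect of one event.** All events below are taken as definitely unrelated, and the Grade 3 events as non-serious.

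| N | Subjects with events | Counted under criterion 3 | As written | With *Grade 3 or higher* |
|---|---|---|---|---|
| 27 | 3 with Grade 3 | 3/27 = 11.1% | Met | Met |
| 27 | 2 with Grade 3, 1 with Grade 4 | 2/27 = 7.4% | Not met | Met (3/27) |
| 54 | 6 with Grade 3 | 6/54 = 11.1% | Met | Met |
| 54 | 5 with Grade 3, 1 with Grade 4 | 5/54 = 9.3% | Not met | Met (6/54) |

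In each pair, the set with the worse event is the one that does not trigger the rule.

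**Step 4: another denominator.** If the denominator is subjects treated so far, the counts fall: 1/10 = 10%, so one event is enough up to 10 subjects, and 2/20 = 10%, so two are enough up to 20. The gap remains. At 10 treated subjects, one unrelated Grade 3 event meets the criterion and one definitely unrelated Grade 4 or 5 event does not.

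**The case against.** The strongest reply is that little turns on this in practice. Any Grade 4 or 5 event that might be related already halts the study at one case. What is left is events judged definitely unrelated to a seven-day topical cream, and for these to change the outcome the trial must be one subject short of the threshold or have such events in 10% of subjects on their own. Safeguards also exist outside the rule. Every serious event "will undergo expedited reporting to the NIAMs and the Independent Safety Officer through KAI within 48 hours" of the investigator learning of it (Section 12.5), NIAMS makes the final attribution for safety reporting (Section 12.3.2), the Medical Monitor decides on each serious-event report (Section 12.8.1), and the list in Section 11.5 does not claim to be exhaustive. All of this is right, and it is why the point is minor. But these are reporting and discretion. None is a halting criterion that counts the events in question.

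A second reply is that a life-threatening or fatal event would ordinarily also fit the functional description of Grade 3, so a Safety Officer would count it anyway. That is probably what was meant. It supports the edit, because a halting rule should not rely on readers supplying missing words.

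A third is that halting for events agreed to be unrelated has limited value, and the inconsistency could equally be removed by adding an attribution condition to criterion 3. Adverse events are recorded from consent (Section 12.2.1), and screening can start 60 days before dosing (Section 8.3), so some added events could precede any cream. This stands as a fair alternative. However, the plan already counts unrelated Grade 3 events, and while it does so there is no evident reason to leave out worse ones.

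Finally, the plan does not itself describe criterion 3 as a protection against wrong attribution. That purpose is inferred from its having no attribution condition.

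**Conclusion.** The concern holds on the text. As written, Grade 4 and 5 events assessed as definitely unrelated count toward no halting criterion, while Grade 3 events with the same attribution count toward the third. The rule therefore ranks severity inconsistently, most likely through a drafting slip.

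The practical size is small. Such events should be rare in this population, and what is missing is only the automatic halt. When it does matter, one subject is enough to change the result. The worked counts assume the planned 27 or 54 subjects as denominator; the gap itself does not depend on that choice. The point belongs at the level of something to consider.

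**What to change.** In Sections 11.5, 12.8.2.2 and 12.8.2.2.1, replace *severe (Grade 3)* in the third item with *Grade 3 or higher*. The three places should change together so that the stopping, review and suspension rules stay the same.

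The cost is a few words, with no new data, visits or analyses. The criterion could be met slightly sooner. The only events that newly count toward a halt are those assessed as definitely unrelated, so some additional halts may be followed by review and resumption.

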12.2 Definitions

An adverse event (AE) is any untoward medical occurrence in a subject during participation in the clinical study or with use of the experimental agent being studied. An adverse finding can include a sign, symptom, abnormal assessment (laboratory test value, vital signs, electrocardiogram finding, etc.), or any combination of these.

A serious adverse event is defined by regulatory agencies as one that suggests a significant hazard or adverse event, regardless of the investigator or sponsor's opinion on the relationship to investigational product. This includes, but may not be limited to, any event that (at any dose):

- is fatal
- is life threatening (places the subject at immediate risk of death)
- requires in-patient hospitalization or prolongation of existing hospitalization
- results in persistent or significant disability/incapacity
- constitutes a congenital anomaly/birth defect
- is medically significant, in that it may jeopardize the subject and may require medical or surgical intervention to prevent one of the outcomes listed above.

Any event that does not exactly meet this definition, but in the investigator's opinion represents a significant hazard (eg, emergency room visit or outpatient surgery), can be assigned the "other significant hazard" in regards to reporting serious criteria.

Additionally, important medical events that may not be immediately life threatening or result in death or hospitalization but that may jeopardize the subject or require intervention to prevent one of the outcomes listed above, or result in urgent investigation, may be considered serious. Examples include allergic bronchospasm, convulsions, and blood dyscrasias.

All subjects will receive verbal and written instructions with site contact information for whom to contact if they experience an AE associated with study procedures performed for this protocol or if the subject resumes their protocol-prohibited medication during the washout period.

EXPECTED RISKS

Risks of applying microbial cream (Cetaphil® Moisturizing Lotion mixed with the subject's endogenous bacteria):

1. Skin infection

The likelihood of subjects developing a skin infection is low given that we will be transplanting their non-pathogenic autologous bacteria that have antimicrobial peptide-producing abilities. Since we are transplanting the subject's own endogenous bacteria back onto them, we know that these bacteria are present on the subject's skin at baseline without causing an infection. In addition, the bacteria strains to be transplanted onto the patient will be screened prior to putting it into the AMT cream to ensure that it is not a skin pathogen. The known pathogen *S. aureus* that frequently colonizes AD skin will not even be considered as a potential bacteria to transplant because of its yellow color on mannitol-salt-agar plates, which isolated bacteria will be grown on. Only red colonies (*S. epidermidis*) growing on mannitol-salt-agar plates will be chosen and screened as potential bacteria to be transplanted onto the subject. If anything, we expect the population of *S. aureus* to be reduced with the use of the AMT cream, since the AMT cream will contain only bacteria that are known to inhibit *S. aureus*. Furthermore, we will be applying these bacteria topically and will exam all patients first to ensure that they do not have any cracks or excoriated skin on their arms before we apply it. We will also avoid applying the microbial cream to the hand since the hand would be a likely source of spreading these bacteria onto other surfaces that other people may contact. Should an infection occur (or should the subject be concerned about an infection), the subject should call Drs. [name] or [name]. The subject would be treated according to the standard treatment after examination by Drs. [name] or [name]. The treatment will include topical and/or oral antibiotics (for infection) depending on the severity of the infection clinically, and Cetaphil® moisturizing lotion (for irritation and dryness), provided by Drs. [name] or [name]. The topical antibiotic of choice will be mupirocin. The oral antibiotic of choice will depend on the individual subject's medical history, including any possible contra-indications to certain medications due to allergies or other concomitant medication use, but doxycycline will be the first line oral antibiotic, followed by a cephalosporin or penicillinase-resistant penicillin.

If the subject calls to report a possible infection during a time when the clinic is closed, the subject will be directed to the resident on call or closest urgent care facility for further management.

2. Risk of medication withdrawal: Discontinuation of a person's AD medication prior to participating in this study and also the prohibition of using AD medications for periods of time during this study may result in worsening or temporary flaring of the patient's AD.

As listed in the inclusion/exclusion criteria (section 10), subjects with severe AD who may have difficulty tolerating periods without medication use will be excluded from participating. Subjects enrolled in the study will be able to use over-the-counter moisturizers as needed. Moisturizers play a role in helping to prevent and control AD flares, and therefore may be of use to subjects whose AD is worsening. The time during which subjects are unable to treat their AD during the study will be limited to the 7-days prior to each screening and treatment/follow-up visit for topical medications, and 28-days prior to each screening and treatment/follow-up visit for oral medications. If for some reason severe worsening of AD occurs during a time in the study that subjects are not permitted to use their medication, the subject will be permitted to use their medication, however the upcoming visit must be rescheduled so that the required 7-day and 28-day wash-out periods before each screening and treatment/follow-up visits are observed. Since the visit dates for the study are relatively flexible (the only real time-dependent visit is the Follow-up Visit, which must occur approximately 24 hours after the Treatment Visit), rescheduling subject visits should not affect study results. AD itself is a chronic condition characterized by periods of flaring and remission. Any worsening of the subject's AD would constitute a disease flare that should be correctable with the use of medications. Flares of AD do not result in permanent deterioration of the subject's

condition. Finally, topical medication discontinuation must only be observed on the subject's bilateral arms since this is the site being studied during the trial. Subjects may treat the AD on all other body surfaces with topical medications throughout the study.

3. Risk of loss of confidentiality: Every reasonable effort will be made to keep records confidential. Research records will be stored in a secure building under lock and key of the study personnel. Data stored in our computers are password protected. Unless required by law, only the Study Doctors, the Study Team, and the UCSD Institutional Review Board will have access to confidential data which identifies subject by name. Because of the need to give these parties access to this information, absolute confidentiality cannot be guaranteed.

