The AMT cream will be provided in single-dose sealed containers. The cream should be stored at room temperature per USP definition of "controlled room temperature" for up to one week. The AMT cream is meant to be applied topically two times a day at a dose of 3×10^7 CFU/ gram Cetaphil®.

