6.2. Study Design – dose schedule

The dosing schedule for the AMT cream or the Vehicle (Cetaphil® lotion) is described in Sections 8.3 and 8.5.

The first dose of the AMT cream or Vehicle cream will be administered to the subjects at the clinical site on Day 0 (Treatment Initiation Visit). At that time, they will be guided and given a handout instructing them to apply the AMT or Vehicle cream uniformly across both arms (this area will include *S. aureus* colonized lesions as well as non-lesional skin) twice daily for seven days. The participants will also be provided a subject diary and 18 single-use containers for dosing at home. An additional 14 single-use packets of AMT Product or Vehicle Product will be dispensed at the next clinic visit on Day 4 to use until Day 7. Subjects will be instructed that 2 additional single-use containers will be provided to them at Day 0 and Day 4 in the event that the subject should misplace a container of study cream. Accountability of the study creams will be performed, and subjects will be asked to return the jars of used and unused cream at the next in-clinic visit.

At the clinic visits on Day 4 and Day 7, the subjects will provide skin swab samples and be assessed for adverse events (AEs). Three additional clinic visits will be scheduled to assess safety and stability of the AMT cream. There will be a 30 day follow-up of all participants after the last treatment to assess safety and disease status. This will be brief phone call, and subjects will be asked to report any new adverse events and to answer questions regarding the status of their AD. Any subject with an ongoing AE/SAE at the time of this phone contact will continue to be followed until the event is resolved with or without sequelae.

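### Section 12.2 makes sites postpone follow-up visits for washout after AD rescue, which takes the primary swab off cream if rescue falls on Days 4-7

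*Combined protocol and SAP*

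**What the plan says.** Section 12.2, under the expected risk of medication withdrawal, provides that if "severe worsening of AD occurs during a time in the study that subjects are not permitted to use their medication", the subject may use it after all, but "the upcoming visit must be rescheduled so that the required 7-day and 28-day wash-out periods before each screening and treatment/follow-up visits are observed". Follow-up visits are named. The reason given is that "the only real time-dependent visit is the Follow-up Visit, which must occur approximately 24 hours after the Treatment Visit", and the section concludes that moving visits should leave the results unaffected. For topical drugs the restriction is local: "topical medication discontinuation must only be observed on the" arms.

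The rest of the protocol describes a different schedule:

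- **Visits (8.3, Table 1).** After Day 0, with optional visits at 1 and 4 hours, clinic visits fall on Days 4, 7, 8, 9 and 11. Visit 5 (Day 7 +/- 7) is tied to a point about four hours after the final application.
- **Endpoints (13.2).** The primary endpoint is the change in *S. aureus* after seven days of cream. Secondary endpoints include swabs one, two and four days after the cream stops.
- **Supply (6.2).** Subjects receive "18 single-use containers for dosing at home" on Day 0. A further 14 "will be dispensed at the next clinic visit on Day 4 to use until Day 7".
- **Washouts (4.3, 7.2).** These are defined relative to the Treatment visit only.
- **Other rescue text.** Section 7.3 covers infection only. Section 8.3 tells subjects to withhold AD medication until after Visit 8.

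**The concern.** The rule rests on a premise that does not fit this trial. A single 24-hour readout matches the single-application pilot in section 1.4, so the paragraph looks carried over. Here Visits 5 to 8 all have a meaning fixed by time since the last application, and delaying one changes what it measures. A swab taken days or weeks after the cream has ended does not measure abundance at the end of treatment.

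The instruction is mandatory, and 12.2 is the only place that says what follows rescue for an AD flare. A site that obeys it breaks the Visit 5 timing in 8.3; a site that keeps that timing breaks 12.2. With 18 and 9 subjects planned, it should be settled beforehand how such a subject's primary value is obtained.

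**Working it through.** **1. When the cream ends.** Section 8.3 (Visit 3) specifies one container per arm per application, so use is 2 arms x 2 a day = 4 containers a day. Section 6.2 adds spares: "2 additional single-use containers will be provided to them at Day 0 and Day 4".

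- Day 0: 4 days x 4 + 2 = 18, as stated.
- Day 4: 3 days x 4 + 2 = 14, as stated.

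The planned supply therefore ends on Day 7. Using the Day 4 spares as well gives 14/4 = 3.5 days instead of 3.0, which does not reach Day 11. Section 6.1.1.1 also limits room-temperature storage, "for up to one week. The AMT cream is meant to be applied topically two times a day", so even cream made on Day 4 expires by Day 11. No text extends dosing when Visit 5 moves.

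**2. Rescue on Days 4-7.** Assume one day of rescue on day d, Visit 4 held on Day 4 before any rescue that day, Day 7 rescue before the Visit 5 swab, and cream ending on Day 7.

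- Earliest compliant Visit 5 = d + 7 (arm-topical) or d + 28 (oral).
- Days off cream = visit day - 7.
- Last day of the Visit 5 window = 7 + 7 = Day 14.

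| Rescue day | Arm-topical Visit 5 | Days off cream | Oral Visit 5 | Days off cream | Days past Day 14 |
|---|---|---|---|---|---|
| 4 | 11 | 4 | 32 | 25 | 18 |
| 5 | 12 | 5 | 33 | 26 | 19 |
| 6 | 13 | 6 | 34 | 27 | 20 |
| 7 | 14 | 7 | 35 | 28 | 21 |

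Longer rescue moves every date later. Section 12.2 does not name antihistamines; with the 7-day washout in 7.2 they would follow the arm-topical column if counted.

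**3. What the dates mean.** An arm-topical delay stays inside the window, so by date alone it looks on schedule, although it departs from the four-hour timing and is arguably a deviation under 15.1. An oral delay cannot satisfy both the washout and the window. It also passes the Visit 8 limit (11 + 7 = Day 18).

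**4. Rescue on Days 1-3.** Read literally, the upcoming visit is Visit 4, the resupply visit. It moves to Day 8-10 (arm-topical; limit 4 + 5 = Day 9) or Day 29-31 (oral). If the washout is instead applied directly to Visit 5, that visit takes those same dates. Under the literal reading the date of Visit 5 depends on whether cream may be dispensed without Visit 4 and whether the course may be extended. The protocol is silent on both, so no Visit 5 date is derived here.

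**The case against.** The strongest reply is that the path is narrow. Section 4.3 excludes severe AD likely to worsen off medication. Rescue must be on the arms or by mouth and must fall within about one week, against the 8.3 instruction to withhold medication. Section 6.6 lets the investigator stop the cream for severe worsening, and 11.2 and 11.3 allow withdrawal and replacement. This stands as to frequency. It does not remove the conflict, because those options are discretionary and the rescheduling is not. If the cream is stopped early, Visit 5 is off cream whatever 12.2 says; the fix has to cover that case.

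It can also be said that the Day 7 +/- 7 window already tolerates swabs on Days 11-14 with no rescue at all. That is true, and the fix leaves the window as it is. But the window only permits those dates, whereas 12.2 compels them.

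A third reply is that washing out before swabbing avoids measuring recently medicated skin. That is a legitimate aim before Day 0. Afterwards it is met by giving up the time point that defines the endpoint.

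Two stronger readings are tempting and not supported:

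- **The intention-to-treat comparison takes in an off-treatment value.** Sections 13.4.1 and 13.4.2 say who is included, not which swab counts. A rescheduled swab might be used or treated as missing.
- **The bias can be sized.** A reader might calculate that one of 18 AMT subjects back at baseline would reduce the planned difference of 192.86 - 19.186 = 173.67 CFU/cm² by 173.67/18 = 9.65, or 5.6%. Both the affected subject and the return to baseline are invented.

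**Conclusion.** The rule is wrong as written. Its rationale refers to a visit this trial does not have, and following it after rescue on Days 4-7 puts the primary swab 4-7 days (arm-topical) or 25-28 days (oral) after the cream ends. The dates are minimums under the assumptions in the working, chiefly one day of rescue and a subject who stays in the study. Rescue on Days 1-3 would also disturb the schedule, by an amount that depends on how resupply is handled. Few subjects are likely to be affected, but neither their number nor the direction or size of any bias can be obtained from the documents. The supported conclusion is a conflict between 12.2 and 8.3 with no handling rule, not a demonstrated distortion of the primary comparison.

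**What to change.** - In 12.2, limit washout-rescheduling to screening and the Day 0 Treatment visit, consistent with 4.3 and 7.2.
- Delete the statements that only the 24-hour visit is time-dependent and that rescheduling should not affect results.
- Keep the Visit 4-8 swabs at their scheduled times whether or not rescue is used; if cream is stopped early, swab on the planned day.
- Record rescue drug, body site and date.
- State in section 13 that on-schedule swabs enter the intention-to-treat analysis, with a supportive sensitivity analysis excluding post-rescue swabs in either arm.

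The cost is protocol wording and one extra analysis; Table 1 already collects concomitant medications at Visits 4-8. The downside is that some swabs will come from recently medicated skin, and if placebo subjects need more rescue the contrast could shrink. The sensitivity analysis addresses this only in part, because excluding post-rescue swabs selects on an event after randomisation. It should not be presented as showing whether bias is present.
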